#### 9.5.3.2.2 Effective gain

Effective gain is a calculation and is defined as the aided threshold relative to the BC (unmasked bone conduction) threshold and is calculated as the difference in dB between aided sound field thresholds and unmasked BC thresholds for the implanted ear. In this investigation, effective gain can be calculated for frequencies 250, 500, 1000, 2000, 3000, 4000, 6000, 8000 Hz. The average effective gain (PTA4) is calculated as the average of frequencies 500, 1000, 2000 and 4000 Hz.

### 9.5.3.3 [REDACTED]

### 9.5.4 Patient Related Outcomes (PRO)

#### 9.5.4.1 Speech Spatial and Qualities of hearing scale (SSQ)

[figure not shown]
A reduced version of the Speech, Spatial and Qualities of Hearing Scale (SSQ) questionnaire [3], the SSQ12,

	Title Clinical Investigation Plan BC114	Document no Doc-00117705	Revision 4	Page 24(39)
---	---	------------------------------------	----------------------	-----------------------

will be used in this investigation. The SSQ12 was developed and validated by Noble, Jensen [4] and contains 12 questions that reflect the perceived performance in speech intelligibility, spatial abilities, and sound quality. Each item is scored from 0 to 10, with larger values always indicating greater ability. The SSQ12 will be assessed at visit 1 (own device) and at visit 2 (Sentio 1).

#### 9.5.4.2 Preference questionnaire

The preference scheme is developed by Oticon Medical and has often been used when comparing two devices.

The preference scheme will be filled out by the subjects at the final visit (Visit 2).

## 10 MONITORING

During the investigation, representatives from Oticon Medical will have regular contacts with the investigational site with the purpose to oversee the investigation. Monitoring activities, including on-site visits, will be performed by appointed monitors according to applicable standards (i.e., ISO 14155) and internal guidance documents. The overall purposes of the monitoring are to ensure that:

- The rights, safety and well-being of human subjects are protected.
- Reported data are accurate, complete, and verifiable from source documents.
- The conduct of the clinical investigation complies with the approved CIP, subsequent amendments (if any), applicable standards (i.e., ISO 14155), and applicable regulatory and ethics committee requirements.

The monitor or other Sponsor personnel will be available between visits if the PI or other site personnel needs information and/or advise.

Authorized representatives of the Sponsor and/or Regulatory Authority may visit the site to perform audits/inspections, including source data verification.

The PI should guarantee access to source documents for the monitor and auditors as well as for inspection by appropriate Regulatory Authority and Ethics Committee, if required.

Source documents are further described in section 12. Data Management.

### 10.1 Monitoring Plan

The extent and nature of the monitoring activities (e.g., review of data entered in the eCRF, source data verification, review of investigator's site file etc.) will be described in an investigation specific Monitoring Plan. The monitoring strategy will be based on a risk-based approach according to ISO 14155:2020.

## 11 STATISTICAL DESIGN AND ANALYSIS

The statistical analysis of all efficacy variables will be performed according to the study Statistical Analysis Plan. The general methodology for the analysis of primary, secondary, and tertiary endpoints is described below. Wilcoxon signed-rank test will be used to test hypotheses. The decision of the hypothesis test is done at the 5% significance level. Pearson's correlations (or Spearman's if the data is not normally distributed) will be used to test correlations.

The distribution of continuous variables will be given as Mean, 95% confidence interval (CI) of the mean, standard deviation (SD), Minimum and Maximum (Mean (SD), (Min; Max)). The distribution of categorical and dichotomous variables will be given as number and percentage (n = (%)).

All subjects that consented to the investigation will be included in the safety population; all subjects enrolled and treated in the investigation will be included in the Intent-to-Treat (ITT) population. All subjects included in the investigation with no major protocol deviations will be included in the Per-Protocol (PP) population. The final decisions regarding the PP population will be taken after investigation completion, at the Clean File meeting before the database lock. All efficacy analyses will be performed on the PP population as main analysis. Complementary analysis for all efficacy variables will also be performed on the ITT population.

Details will be described in the Statistical Analysis Plan.

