### 8.2 Secondary Objective(s)

Secondary objective(s)	Corresponding secondary endpoint/outcome variable(s)	Section
B. To assess the improvement of hearing with the Sentio1.	1. Functional gain with Sentio 1, i.e., the difference in dB between unaided and aided sound field thresholds, for all measured frequencies.	9.5.3.2.1
C. To assess self-reported performance with the Sentio 1 compared to previous sound processor after at least one month field usage of the Sentio 1	1. Average SSQ12 scores with Sentio 1 for each question, sub-scales and in total. 2. Average SSQ12 scores with current sound processor for each question, sub-scales and in total.	9.5.4.1

	3. Difference in SSQ12 scores between Sentio 1 and current sound processor for each question, subscales and in total.	
D. To assess the preference of sound processor.	1. Percentage (%) of subjects who prefer the Sentio 1 over current sound processor	9.5.4.2
E. To assess the degree to which Sentio 1 compensates for the BC hearing loss	1. Effective gain defined as the difference in dB between aided sound field thresholds with Sentio 1 and unmasked BC thresholds on the aided ear(s). The effective gain is calculated for all measured frequencies. 2. Effective gain with Sentio 1, see definition above, calculated in average for frequencies 500, 1000, 2000 and 4000 Hz (PTA4).	9.5.3.2.2
F. To assess the difference between BC in-situ thresholds measured with Sentio 1 and conventional unmasked BC audiometry.	1. Difference in dB between Sentio 1 BC in situ thresholds and BC thresholds measured with conventional unmasked BC audiometry for the frequencies 500, 1000, 2000, 3000 and 4000 Hz	9.5.3.1 9.5.1
G. Assess safety with the Sentio 1 sound processor	1. Tabulation of AEs occurred throughout the investigation and percentage of individuals with reported AEs.	18

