### 11.3 Missing data handling

Missing data (e.g., single questions, experimental repetitions) will be treated as Not A Number (NANs) and will be disregarded from the analysis. A detailed description of missing data will be given in the Statistical Analysis Plan. Missing data will be handled in the same way for PP and ITT population.

oticon MEDICAL	Title Clinical Investigation Plan BC114	Document no Doc-00117705	Revision 4	Page 26(39)
--------------------------	---	------------------------------------	----------------------	-----------------------

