## 14 DEVIATIONS FROM CLINICAL INVESTIGATION PLAN

A CIP deviation is an intentional or unintentional failure to follow the requirements of the CIP. Every effort should be made to comply with the requirements of the CIP and the Investigator, and other representatives of the investigational site team, is not allowed to deviate from the CIP, unless needed to protect the rights, safety and well-being of the subjects (i.e., emergencies). Under these circumstances, deviations from the CIP may proceed without prior approval by the Sponsor and favourable opinion from EC. Such cases should be documented and reported to the EC, as per local requirements, and to the Sponsor as soon as possible, but in no event later than 5 working days after the emergency occurred.

If other deviations occur, the Investigator should inform the monitor/clinical trial manager and make a record in the CIP Deviation Log provided in the EDC system. The implications of the deviation must be reviewed and discussed between the Sponsor and the Investigator. If deviations are found during monitoring visits, they should also be documented in the monitoring report and handled as above. This should be done as soon as possible after detection to avoid repetitive deviations. Continuous review of protocol deviations during monitoring visits aim to detect systematic errors and to identify retraining needs at the site. Frequency of monitoring is described in the monitoring plan and should be increased if systematic deviations are identified. All protocol deviations must be documented stating the reason, date, the action(s) taken, and the impact for the subjects and/or the investigation. If serious or repeated deviations occur, the Sponsor has the right to initiate early termination of the investigation.

At the end of the investigation, or in connection to a predefined interim analysis, protocol deviations will be re-categorized as minor or major and their consequence on analysis populations will be determined.

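### Does the preference percentage need a planned confidence interval, and a rule for subjects who miss Visit 2?

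*Combined protocol and SAP*

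**What the plan says.** Section 8.2 defines the preference endpoint as "Percentage (%) of subjects who prefer the Sentio 1 over current sound processor". Section 9.5.4.2 fixes when it is collected: "The preference scheme will be filled out by the subjects at the final visit (Visit 2"). Table 2 and section 9.4.1.2 agree, and no later visit repeats it.

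Section 11 sets the summary style. For measurements, "The distribution of continuous variables will be given as Mean, 95% confidence interval (CI) of the mean", with SD and range. For yes/no and categorical variables, "The distribution of categorical and dichotomous variables will be given as number and percentage (n" and per cent), with no interval named.

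On analysis sets, section 11 says that "all subjects enrolled and treated in the investigation will be included in the Intent-to-Treat (ITT) population". The per-protocol set is the main one and excludes major deviations. Section 14 says when these are settled: "protocol deviations will be re-categorized as minor or major and their consequence on analysis populations will be determined".

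On missing values, section 11.3 says "Missing data (e.g., single questions, experimental repetitions) will be treated as Not A Number (NANs) and will be disregarded from the analysis", and then "Missing data will be handled in the same way for PP and ITT population". Sections 11 and 11.3 both leave the detail to a Statistical Analysis Plan, and no separate text of that plan is in the supplied file.

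**The concern.** Two things look wrong at first reading.

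The first is that means and percentages from the same few subjects are treated differently in one paragraph, without a reason. Section 6.2.1.2 gives preference a supporting role in confirming performance, and section 11.1 offers a sample-size rationale for functional gain and SSQ12 but none for preference. A statement such as 82% preferring the new processor sounds firm when it may rest on 9 of 11 people.

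The second is that the sections on timing, missing data and analysis sets combine awkwardly. Preference is asked once, missing values are disregarded, and both analysis sets follow the same rule. A fitted subject who does not attend Visit 2 is a member of the intention-to-treat set but would contribute nothing to its percentage. For this endpoint the intention-to-treat figure would add only attenders excluded from the per-protocol set. If people who disliked the device were the ones who stayed away, both figures would be too favourable and the comparison between them would not show it.

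**Working it through.** **The plan's own numbers.** No figure is stated for preference. The expected number of answers comes from section 11.1: 12 to 14 enrolled, about 15% drop-out, about 11 completing. For functional gain the normal formula gives n = (8 × (1.960 + 1.282) / 9)² = 8.30, so 9 subjects; at n = 11 the paired-t power is 91.9%, which agrees with the stated 90%. Allowing for drop-out, 11 / 0.85 = 12.9, so 13 enrolled, inside the planned range.

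**Width of the omitted interval.** The preference counts are illustrative, because the plan gives no expected rate. The exact (Clopper-Pearson) 95% limits for x of n are the 2.5% point of Beta(x, n − x + 1) and the 97.5% point of Beta(x + 1, n − x).

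| x/n | % | Exact 95% CI |
|---|---|---|
| 9/11 | 81.8 | 48.2 to 97.7 |
| 10/12 | 83.3 | 51.6 to 97.9 |
| 11/13 | 84.6 | 54.6 to 98.1 |
| 12/14 | 85.7 | 57.2 to 98.2 |
| 9/12 | 75.0 | 42.8 to 94.5 |
| 10/13 | 76.9 | 46.2 to 95.0 |
| 11/14 | 78.6 | 49.2 to 95.3 |

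The intervals are wide, and one answer fewer at 12, 13 or 14 answers takes the lower limit below 50%. But 50% is not a line the plan draws, and the crossing depends on the method: the Wilson interval for 9/11 is 52.3 to 94.9%, and for 11/14 it is 52.4 to 92.4%.

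**What the interval would describe.** Section 11.1 screens the complete I1 population (N = 16), and section 4.1 states the purpose as confirming performance in that group. Treat each recipient's preference as a fixed yes or no, and let everyone who did not answer go either way. The share among all 16 then lies between x/16 and (x + 16 − n)/16:

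- 9/11: 9/16 to 14/16, or 56 to 88%
- 9/12: 9/16 to 13/16, or 56 to 81%
- 10/13: 10/16 to 13/16, or 63 to 81%
- 11/14: 11/16 to 13/16, or 69 to 81%

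Every count whose exact interval includes 50% already fixes a majority of the 16. The exact interval answers a question about a wider, unlimited population, which is a different target.

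**Loss before Visit 2.** Assume the 15% drop-out is spread evenly over 24 months (section 9.3.5). Visit 2 falls at 1 to about 2 months (section 6.2).

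- Probability of loss per subject: 0.15 × 1/24 = 0.00625, up to 0.15 × 2/24 = 0.0125.
- Expected number lost: 12 × 0.00625 = 0.075, up to 14 × 0.0125 = 0.175.
- Chance of any loss: 1 − 0.99375^12 = 7.2%, up to 1 − 0.9875^14 = 16.1%.

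If one of 12 fitted is lost, 9/11 = 81.8% has bounds 9/12 = 75.0% and 10/12 = 83.3%. As a ceiling, suppose all drop-out came before Visit 2: 13 fitted, 2 lost, bounds 9/13 = 69.2% and 11/13 = 84.6%. With no loss the shift is zero.

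**The case for a change.** The best argument for a change is that it costs almost nothing. An exact interval needs no new data. The plan already puts intervals around means in these same subjects, so it does treat them as a sample. Section 9.3.2.1 also names a target population wider than the 16 recipients. The even-attrition assumption could be wrong too, since people who dislike a new processor may leave early, and section 9.3.3 collects their reasons without tying them to this endpoint.

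Part of this stands. Section 11 does name an interval only for means. If the report generalises beyond I1 recipients, an interval with its population named would be good practice. Any missing answers should be counted and listed with the withdrawal reasons. An analyst can do all of this under the present wording.

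The rest does not carry a change. Section 11 describes its text as general methodology and leaves the detail to the Statistical Analysis Plan, so absence from the supplied text is not absence from the full plan. The examples in section 11.3 are single questions and repetitions, so extending the rule to a whole missed visit is an inference, and the denominator for preference is not stated either way. Non-attendance would affect SSQ12 with Sentio 1 and functional gain at Visit 2 in the same way, so a special rule for preference would be arbitrary. Assigning best-case and worst-case preferences that nobody expressed is one debatable sensitivity choice. Such a rule would also probably arrive late: 15 November 2022 plus 8 weeks of enrolment, 1 month and 4 weeks is about 10 March 2023, before revision 4 of 4 July 2023.

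**Conclusion.** No change follows. The missing interval is a reporting detail that analysts can fill sensibly: with number and percentage reported, the interval can be computed directly, and it would change no result. Preference carries no hypothesis, and the success criterion in section 8.1.1 rests on functional gain alone. The imprecision is real, with exact intervals 41 to 50 points wide at the illustrative rates of 82 to 86%, but it is visible to anyone shown 9 of 11.

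The non-attender point is conditional on how section 11.3 is applied. It has a 7 to 16% chance of involving anyone under even attrition, and would then lower 82% to 75% at worst for one lost of 12, or to 69% in the extreme case of two lost of 13.

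These sizes rest on illustrative counts, on the stated 15% drop-out and its even spread, and, for the comparison with all 16 recipients, on treating preference as a fixed characteristic of each person. No bias or wrong result has been shown.

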#### 9.4.1 *Clinical Investigation visits*

##### 9.4.1.1 Visit 1 (screening/baseline visit)

Following procedures will be carried out during the first visit. The flow below is a suggested flow, based on convenience for subject and investigator the order may be changed. Information, informed consent and screening will always be carried out before any investigation related procedures are conducted.

- The subject is thoroughly informed about the investigation including all investigation related visits. Time will be given for consideration and answering any questions the subject might have.
- Consent form is signed.
- Screening according to inclusion and exclusion criteria.
- The subject's demographical data as well as their personal data and subjects' characteristics are registered.
- Audiometry is performed
- Fitting and adjustment of the Sentio 1 is performed
  - Including BC in-situ and feedback management measurement.
  - Strength of retention magnet is considered and potentially changed according to the subject's needs and preference.
  - Finetuning is considered and Sentio 1 is adjusted according to the subject's needs and preference.
- [REDACTED]
- Questionnaire for evaluation the subject's current hearing solution is filled out.
- Questionnaires for evaluation of the Sentio 1 is handed out and instructions to fill them out prior to next visit is given.
- AEs are assessed.

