### 11.1 Sample size

The complete population implanted with I1 (N = 16) will be screened for participation in the investigation and the estimated sample size will be 12-14 patients enrolled, about 15% drop-out, and approximately 11 patients completing the study. Data from 11 patients will enable detection of a statistically significant difference between aided and non-aided functional gain of 9 dB or higher (based on normal approximation), with 90% power, 5% two-sided level of significance, and an estimated variability (SD) for the difference of 8 dB. This is considered well within the clinically relevant detection levels for functional gain as described by the systematic literature review on comparable devices [F]. The proposed sample size is also considered to ensure clinically relevant data for conclusions on the secondary end-point SSQ12, where the previous study on the I1 and S2 [A] has used a sample size of 10 patients, and 11 patients would enable detection of statistically significant differences in mean scores of 1 or higher (based on normal approximation), with 90% power, 5% two-sided level of significance, and an estimated variability (SD) for the difference of 0.9.

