### **Case Report Form recording and processing**

Data captured will be recorded, by the investigator and/or delegated site staff, in eCRFs by means of an EDC-system (SMART-TRIAL), provided/hosted by an external party (MEDEI ApS, Copenhagen, Denmark). The system has built-in features that enables users to be GCP and GDPR compliant. All data in relation to SMART-TRIAL is stored on secured Microsoft Azure hardware located in the EU, i.e., Dublin, Ireland. All users of the EDC system have personal accounts, accessed by two-factor authentication, allowing tracking of all data entries and changes in the system (i.e., audit trail).

The set-up, build and maintenance of the eCRF, incl. corresponding content (forms, events, data checks etc.), and testing/validation of the system, is performed by trained Sponsor representatives.

All data, subject- and product-related, must be accurately recorded in a timely manner (i.e., within 5 working days) into the EDC system by the delegated site staff.

NB. For Serious Adverse Events (SAE), Serious Adverse Device Effects (SADE) stricter timelines applies, see Section 18.4 for further reference.

The person entering the data into the database is not allowed to make any personal interpretation or to make any decisions on the data than self-evident corrections as listed in the data entry instructions or data handling report. All entered data must be consistent with the source documents, and if any discrepancies are found they must be corrected or explained in writing where applicable. The Principal Investigator is responsible for the data entered in the EDC-system and for signing the eCRF at the end of the clinical investigation.

The patient reported outcome (PRO) instrument used in this investigation will be completed on paper forms by the subjects themselves. The forms (i.e., source documents), marked with the Subject ID, will then be transferred by manual data entry to the corresponding form in the EDC-system by an authorized member of the investigation site team.

For screening failures following data will be recorded: reason for failure with reference to IE criteria and patient characteristics.

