### 18.2 Methods for discovering and documenting AE/ADE and DD

All subjects will be asked about the occurrence of AEs from the first day and until completion of the investigation. Events prior to enrolment will be considered medical history. The Principal Investigator (PI) or delegate will collect safety information using a non-leading question "have you experienced any new health problems or worsening of any existing condition?". Events directly observed or spontaneously reported by the subjects will also be recorded throughout the investigation

All AEs falling into any of the previously defined definitions must be recorded as an AE in the eCRF. Clearly related signs, symptoms and abnormal diagnostic procedure results should be grouped together and reported as a single diagnosis or symptom whenever possible.

All AEs, but not limited to events reported by the subject or reported in response to an open question by the PI or member of the investigation team, which fall into any of the previously defined definitions must be recorded as an AE in the eCRF and should include the following information:

- Brief description of the event(diagnosis)
- Date of event onset (and time, if relevant)
- Date of event resolution (and time, if relevant)
- Severity
- Seriousness
- Causality assessment (i.e., relationship to medical device and/or procedure)
- Event treatments
- Event outcome

Inadequacy of a medical device with respect to its identity, quality, durability, reliability, safety or performance shall be reported as a device deficiency (DD) without unnecessary delay to the Sponsor by using the device deficiency form. It is the PI's responsibility to record every observed device deficiency together with an assessment. The Sponsor shall review all device deficiencies and determine and document in writing whether they could have led to a SADE. Device Deficiencies that are assessed to or have SADE potential should be subjected to expedited reporting as described in Section 18.4.

AEs/ADEs and DDs should be reported to Sponsor as described in section 18.4.1. SAEs/SADEs/USADEs and DDs with SADE potential should be subject to expedited reporting according to section 18.4.2.

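### The safety population is set by consent alone and endpoint G names no denominator, so a consented but never-fitted subject may be counted in the adverse event percentage for Sentio 1

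*Combined protocol and SAP*

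**What the plan says.** Section 11 defines the analysis sets. For safety: "All subjects that consented to the investigation will be included in the safety population". For efficacy, in the same sentence: "all subjects enrolled and treated in the investigation will be included in the Intent-to-Treat (ITT) population". Section 11 assigns efficacy analyses to the per-protocol set, with ITT as complement, but does not say which set serves endpoint G. It leaves details to a Statistical Analysis Plan whose text is not in the document under review.

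Objective G in section 8.2 is safety with the Sentio 1 sound processor. Its endpoint reads: "Tabulation of AEs occurred throughout the investigation and percentage of individuals with reported AEs". No population is named there, in the synopsis, or in section 18, to which the table refers.

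On the order of events at Visit 1, section 9.4.1.1 says: "Information, informed consent and screening will always be carried out before any investigation related procedures are conducted". Fitting follows later in the same visit.

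Three statements bear on whether AEs would be captured in someone who is never fitted:

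- Section 12, Case Report Form recording and processing: "For screening failures following data will be recorded: reason for failure with reference to IE criteria and patient characteristics".
- Section 18.2, on timing: "Events prior to enrolment will be considered medical history".
- Section 18.2, on who is asked: "All subjects will be asked about the occurrence of AEs from the first day and until completion of the investigation".

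On numbers, section 11.1 says: "The complete population implanted with I1 (N = 16) will be screened for participation in the investigation". Sections 9.3.5 and 11.1 expect 12-14 of these to be enrolled.

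**The concern.** A percentage offered as evidence on the safety of a device should be taken over people who used it. The plan imposes an exposure condition on the ITT set and omits it from the safety set. Exclusion criterion 2 (section 9.3.2) rests on the judgement of the investigator or the medically responsible person, and section 9.3.3 lets a subject leave at any time. A person can therefore sign consent, stop before fitting, and still belong to the safety population.

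Such a person would add one to the denominator but might have little chance of adding to the numerator: AEs are not among the items listed for screening failures, and events before enrolment count as medical history. Section 18.2 nevertheless has all subjects asked from the first day, so an event in an unfitted subject could also be recorded and counted. The percentage can move either way.

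At stake is the reported AE percentage, which feeds the safety conclusion of the final analysis (section 11.2). The efficacy results do not depend on it.

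**Working it through.** The plan gives no AE percentage or denominator, so there is no stated figure to reproduce. The check asks how far the percentage can move.

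**Inputs from the plan**

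- Candidates screened: 16 (sections 9.3.5 and 11.1).
- Enrolled: 12-14, taken here as the number fitted, n.
- Screened but not enrolled: 16 − 14 = 2 to 16 − 12 = 4.

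**Assumptions, because the plan is silent**

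- k = number consented but never fitted. Refusal of consent could account for all 2-4 non-enrolled candidates, since signed consent is itself inclusion criterion 1 (section 9.3.1). So k runs from 0 to at most 16 − n.
- a = number of fitted subjects with at least one AE; a = 3 is used for illustration.

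**Case 1: unfitted subjects have no recorded AE**

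The percentage falls from a/n to a/(n + k). The relative reduction is 1 − n/(n + k) = k/(n + k), whatever the value of a, provided a > 0.

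| n fitted | k = 1 | k = 2 | k = 3 | k = 4 |
|---|---|---|---|---|
| 12 | 1/13 = 7.7% | 2/14 = 14.3% | 3/15 = 20.0% | 4/16 = 25.0% |
| 13 | 1/14 = 7.1% | 2/15 = 13.3% | 3/16 = 18.8% | – |
| 14 | 1/15 = 6.7% | 2/16 = 12.5% | – | – |

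The last entry in each row is the extreme in which all 16 candidates consent. It is an upper bound, not an expectation.

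In percentage points with k = 1, the shift is 100 × a/(n(n + 1)): 100/(12 × 13) = 0.64 per affected subject at n = 12, and 100/(14 × 15) = 0.48 at n = 14. With a = 3:

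- n = 12: 3/12 = 25.0% becomes 3/13 = 23.1%, a fall of 1.9 points.
- n = 14: 3/14 = 21.4% becomes 3/15 = 20.0%, a fall of 1.4 points.

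**Case 2: the one unfitted subject has a recorded AE**

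The percentage goes from a/n to (a + 1)/(n + 1). With a = 3:

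- n = 12: 25.0% becomes 4/13 = 30.8%, a rise of 5.8 points.
- n = 14: 21.4% becomes 4/15 = 26.7%, a rise of 5.2 points.

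In general the percentage rises when the share with AEs among unfitted subjects exceeds a/n, and falls when it is below.

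**Case 3: no AEs at all**

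The percentage is 0 under either denominator, but the exact (Clopper-Pearson) 95% upper limit is not: 26.5% for 0/12, 23.2% for 0/14 and 20.6% for 0/16. Again, 16 is the extreme.

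**Case 4: k = 0**

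Both denominators coincide and nothing changes.

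**The case against.** The strongest reply is that a consent-based set is a legitimate choice that fits the plan's own AE framework. Section 18.1.1 defines an AE as arising in the context of the investigation, related to the device or not, and includes events tied to study procedures. Endpoint G counts events throughout the investigation, and collection starts on the first day. Each AE is also coded for its relationship to device and procedure (section 18.2.2), so device-related events remain identifiable. This stands for collecting and listing events: the consent-based set loses none. It does not stand for the percentage, because causality coding acts on the numerator only.

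A second reply is that the harm needs two things the plan does not establish: that G uses the safety set, and that someone consents without being fitted. Both limits are real. Consent, screening and fitting fall in one visit, the criteria are few, and the candidates are a closed, already implanted group, so k may well be 0. For that reason the point is about what the rule permits.

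A third reply is that the Statistical Analysis Plan may settle the denominator. It may. But section 11 already fixes the safety set by consent, and an analysis plan that follows it inherits the gap unless it names another denominator for G.

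Finally, the shift is small beside the sampling uncertainty: the exact 95% interval is 5.5% to 57.2% for 3/12 and 5.0% to 53.8% for 3/13. That is a fair argument about severity. It gives no reason to keep never-exposed people in the figure.

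**Conclusion.** The concern holds, at minor severity. As written, the rule can produce an AE percentage for the Sentio 1 that includes people who never wore it.

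With one such subject the effect is a relative dilution of 6.7% to 7.7% if that subject has no AE, or, with three affected fitted subjects, a rise of 5.2 to 5.8 points if the subject has one. If all 16 candidates consented, which is unlikely, the dilution would be 12.5% to 25%. If every consenting subject is fitted, the effect is nil.

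This rests on three assumptions: the safety set is the denominator for G, which is the natural reading but is not written; k is at least 1; and the number fitted equals the 12-14 planned for enrolment. The primary hypothesis test, type I error, power and the success rule in section 8.1.1 are not affected, because safety is reported descriptively.

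**What to change.** In section 11 and in the Statistical Analysis Plan, state that the denominator for endpoint G is all subjects fitted with the Sentio 1 at least once, either by redefining the safety population or by naming this denominator for G alone. List separately any AE in a consented subject before fitting or without it, so that no event is lost. It would help to say at the same time whether AEs are recorded for screening failures, since sections 12 and 18.2 leave that open; this is only a clarification.

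The cost is one sentence in each place and one short listing. The AE percentage may come out slightly less favourable than under the consent-based denominator. If every consenting subject is fitted, no result changes.
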